9.7.1.1.2 SECONDARY ENDPOINTS

The secondary endpoints of the study are:

- Time to worsening of CDR scores by 24 months (eg, the worsening of global CDR score is defined as an increase from baseline by at least 0.5 points on the global CDR scale on 2 consecutive scheduled visits at which global CDR is undertaken)
- Time to conversion to dementia for subjects who were not clinically staged as dementia at Baseline based on clinical diagnosis
- The rate of change over time (mean slope) based on CDR-SB score over 24 months
- Change from baseline in CDR-SB at 27 months (ie, 24 months of treatment plus 3 months posttreatment follow-up) (revised per Amendment 01)
- Change from baseline in ADAS-cog₁₄, MMSE, and FAQ at 24 months
- Change from baseline in ADAS-cog₁₄ Word List (immediate recall and delayed recall) at 24 months (revised per Amendment 01)

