9.7.1.6.2 SECONDARY EFFICACY ANALYSES

The secondary analyses will be performed only if the primary analysis is significant. The treatment effect for elenbecestat (E2609) 50 mg/day versus placebo, for each secondary efficacy endpoint, will be tested using a sequential testing procedure at a significance level of 2-sided $\alpha = 0.05$, ie, any test will start only if the test with higher hierarchical order is significant. The final hierarchical order will be specified later in the statistical analysis plan before database lock.

Time to worsening of CDR scores by 24 months will be analyzed on the FAS using Cox regression model for treatment effect adjusting for randomization stratification factors. Time to worsening of a CDR score is defined as time from randomization to worsening of the CDR score (ie, the first worsening in 2 consecutive scheduled visits). For subjects whose CDR scores have not worsened by the end of study, the time to worsening of the CDR score will be censored at the date of last CDR assessment for these subjects.

Time to conversion to dementia for subjects who were not clinically staged as dementia at Baseline based on clinical diagnosis will be analyzed on the FAS using Cox regression model for treatment effect adjusting for randomization stratification factors. Proportion of subjects with dementia diagnosis at 24 months will be estimated using Kaplan—Meier method based on time to conversion to dementia based on clinical diagnosis. Time to conversion to dementia for subjects who were not clinically staged as dementia at Baseline based on clinical diagnosis is defined as time from randomization to conversion to dementia based on clinical diagnosis. For subjects without clinical dementia by the end of study, the time to conversion to dementia based on clinical diagnosis will be censored at the date of last dementia diagnosis.

The rate of change over time (mean slope) based on change from baseline in the CDR-SB will be analyzed using linear mixed effects (LME) models for multivariate normal data derived from a random coefficient model (slope analysis), where the mean slope in each group depends on a continuous assessment time. The LME model will include baseline CDR-SB, randomization stratification variables, assessment time, and treatment group-by-assessment time.

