The other continuous secondary efficacy endpoints as defined above will be analyzed using the same MMRM model as the primary efficacy analysis to compare elenbecestat (E2609) 50 mg per day versus placebo on the FAS, using baseline value corresponding to the response variable in the model.

The relationship between clinical changes at 24 months (CDR-SB, ADAS-cog₁₄, MMSE, and FAQ) and changes in each of the biomarkers (amyloid PET, tau PET, CSF A β (1-42), t-tau, p-tau, vMRI, and fMRI) at 24 months, will be evaluated using an ANCOVA model. (revised per Amendments 01, 04, and 05) Changes in clinical scales at 24 months will be the response variables and either continuous or categorical change of biomarkers will be independent variables. The ANCOVA model will also include baseline value for clinical scale as a covariate, randomization stratification variables, treatment group as factors, and other terms as appropriate.

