In the event that a subject develops moderate to severe oral or genital herpes, study drug administration should be interrupted for a maximum period of 4 weeks. Subjects who develop a mild case of oral or genital herpes may remain on study drug even if the event lasts more than 72 hours. Subjects who recover from moderate to severe oral or genital herpes within 4 weeks may resume treatment if it is deemed appropriate by the investigator after consultation with Medical Monitor. Subjects should permanently discontinue study drug if the oral or genital herpes has not resolved within 4 weeks or returns during rechallenge. (revised per Amendment 03) Subjects who discontinue study drug early must complete the ED Visit (within 7 days of the last dose of study drug) and the Follow-Up Visits (1 and 3 months after the last dose of study drug). These Follow-Up Visits will be conducted to monitor efficacy and safety parameters after early withdrawal from the study or discontinuation of study drug.

All subjects who discontinue study drug before reaching 12 months of treatment will also be asked to return to the clinic for a 12-month clinical assessment and then again at 24 months. Subjects who discontinue treatment between 12 and 24 months of treatment will be asked to return to the clinic for a 24 month clinical assessment. Subjects who discontinue early from study drug are considered “on study” as long as they continue to return for their regularly scheduled clinical assessments at 12 and 24 months as outlined above, at which efficacy and quality of life will be assessed along with concomitant medications and AEs. However, subjects who discontinue study drug early are not considered to have ‘completed’ the study as a final Subject Disposition.

The primary reason for discontinuation and all other reason(s) contributing to the subject’s discontinuation from study drug(s) should be collected on the ED from study drug electronic case report form (eCRF) page. In addition, the date of last dose of study drug(s) will be recorded on the Study Drug Dosing eCRF page. If a subject discontinues study treatment and the study at the same time, the end-of-study procedures (Final Visit) will be followed (see [Section 9.5.5](#)).

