[Morris et al., 1989](#)), (cited by [Mohs et al., 1997](#)). For Word Recall, 10 words, each printed in large letters on 1 card, are shown one at a time for 2 seconds each. The subject is instructed to read the words aloud. Immediately after reading the list, the subject is asked to recall the list aloud. This procedure is repeated 3 times and the immediate memory score is the average number of words incorrectly recalled during 3 trials. Word Recall is administered near the beginning of the ADAS-Cog₁₄. A few minutes later, the subject is asked to recall as many words as possible from the previously studied list. The total number of words incorrectly recalled on this Delayed Word Recall task ranges from 0-10. (revised per Amendment 03)

FAQ: The study partner provides performance ratings (from 0 to 3) on 10 complex activities of daily living performed within the preceding 4 weeks. Scores range from 0 (independent) to 30 (dependent).

Audio recordings will be made during the administration of a number of the scales above for possible central review (as permitted by local regulations).

9.5.1.3.2 vMRI AND fMRI

vMRI will be used to evaluate disease modification as indicated by measurements of brain atrophy, including the change from Baseline in terms of the measured hippocampal volume based upon the centralized measurement of the structure on repeated MRIs. A large number of studies, including the AD Neuroimaging Initiative, have shown that quantitative measurements of hippocampal, whole brain, and total ventricular volume provide robust and reliable biomarkers of disease progression, and potential for assessment of PD efficacy.

vMRI sequences will be collected for all subjects immediately following all safety MRI scans in the same imaging session. vMRI will be conducted at either 1.5T or 3T, and across multiple scanner types and the type of scanner used will be documented. vMRI analysis will be performed by a central imaging laboratory on MRI scans obtained at the times specified in [Table 3](#) and [Table 4](#), according to standard quality control and normalization procedures for measurements of the whole brain and total ventricular volume. Measurements of the right and left hippocampal volumes will be based on a validated algorithm and conducted in the same laboratory. Additional analysis of regions of interest and cortical thickness may also be performed.

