^b Subjects who discontinue taking study drug prematurely for any reason will undergo an ED Visit within 7 days of their last dose of study drug. In addition, Follow-Up Visits will be scheduled 4 and 12 weeks after the last dose of study drug (Visit 14 and Visit 15, respectively). Subjects who discontinue study drug before reaching 12 months of treatment will also be asked to return to the clinic for a 12 month clinical assessment and then again at 24 months. Subjects who discontinue treatment between 12 and 24 months of treatment will be asked to return to the clinic for a 24 month clinical assessment. Subjects who discontinue early from study drug are considered “on study” as long as they continue to return for their clinical assessments at 12 and 24 months as outlined above, at which efficacy (MMSE, CDR, ADAS- cog₁₄) and quality of life (EQ-5D, QOL-AD and Zarit’s Burden Interview) will be assessed along with concomitant medications and AEs. These 12 and 24 month clinical assessment visits do not need to be attended if they fall within 8 days (visit window) after the ED Visit or within ±8 days of either of the Follow-Up Visits (Visit 14 and Visit 15).

- ^c All subjects, regardless of whether they complete all 24 months of treatment or discontinue study drug prematurely, will complete 2 posttreatment Follow-Up Visits; one 4 weeks after the last dose of study drug and a second 12 weeks after the last dose of study drug (Visit 14 and Visit 15 respectively). If clinically indicated, more frequent safety assessments can be made as UNS assessments or visits during the posttreatment Follow-Up Period. Subjects who have a Grade 2 or greater lymphocytopenia (less than 800/mm³) during the follow-up period (ie., at either Visit 14 or Visit 15) should have ALC measured every 4 weeks until resolution or confirmation of a non drug-related cause of the lymphocytopenia. ALC will be derived from the complete blood count (CBC) with differential representing the normal lymphocytes (with atypical lymphocytes removed and presented as a separate count if they are present) and calculated by the white blood cell count × percentage of lymphocytes. (revised per Amendments 01 and 02) (revised per Amendments 01 and 02)

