- ^m Blood samples will be collected and stored. These samples may be used for exploratory analyses, in the event that the subject develops treatment-emergent adverse events that warrant further investigation (eg, treatment-emergent infection), these samples may be tested to determine whether the subject already had prior exposure to any suspected infective agents. (revised per Amendment 04)
- ⁿ The subject components of these assessments are to be completed in the morning whenever possible, or consistently at the same time of day. Ideally, the subject component of these assessments should be completed before more invasive assessments or procedures (eg, physical examination, ECG, blood draws). The FAQ is to be administered to the study partner. At visits where the CDR or FAQ are conducted, the investigator will determine whether the study partner must attend in person or whether telephone contact will be suitable, and will base this determination upon the functional ability of the subject among other factors. For any given subject, every effort should be made to ensure that the CDR rater remains unchanged throughout the study. (revised per Amendment 04)
- ^o Disease staging will be performed every 3 months. The site clinician is required to confirm the staging of disease, ie for subjects who were, at Screening, not clinically staged as dementia, does the subject still meet the definition of MCI due to AD or have they progressed into the stage of clinical dementia. For any given subject, every effort should be made to ensure that the diagnosing clinician (responsible for the initial diagnosis and for disease staging) remains unchanged throughout the study. (revised per Amendment 04) This staging decision will be verified via a central review process and adjudicated if necessary. Adjudication will only occur when there is a discrepancy between the diagnosis and clinical disease staging made by the site compared to that determined by the central review process; moreover, where adjudication is required, it will be undertaken by an independent assessor(s). (revised per Amendment 01)
- ^p The clinical assessment of suicidality will require input from both the subject and the study partner
- ^q There are 3 separate administrations of the EQ-5D as follows: (1) in the subject by self report, (2) in the study partner by self report, (3) in the subject by proxy using the study partner (revised per Amendment 02)

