9.7.1.1.2 SECONDARY ENDPOINTS

The secondary endpoints of the study are:

- Time to worsening of CDR scores by 24 months (eg, the worsening of global CDR score is defined as an increase from baseline by at least 0.5 points on the global CDR scale on 2 consecutive scheduled visits at which global CDR is undertaken)
- Time to conversion to dementia for subjects who were not clinically staged as dementia at Baseline based on clinical diagnosis
- The rate of change over time (mean slope) based on CDR-SB score over 24 months
- Change from baseline in CDR-SB at 27 months (ie, 24 months of treatment plus 3 months posttreatment follow-up) (revised per Amendment 01)
- Change from baseline in ADAS-cog₁₄, MMSE, and FAQ at 24 months
- Change from baseline in ADAS-cog₁₄ Word List (immediate recall and delayed recall) at 24 months (revised per Amendment 01)

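### The schedule for off-drug 12- and 24-month visits provides no disease staging and leaves out the FAQ, so two secondary endpoints lose data on discontinuers who attend

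*Protocol*

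**What the plan says.** Section 9.7.1.1.2 of the protocol lists among the secondary endpoints the change from baseline in ADAS-cog14, "MMSE, and FAQ at 24 months", and also "Time to conversion to dementia for subjects who were not clinically staged as dementia at Baseline based on clinical diagnosis". Under Section 9.7.1.6.2 the secondary efficacy endpoints are tested in sequence. Continuous ones such as the FAQ "will be analyzed using the same MMRM model as the primary efficacy analysis", on the FAS. For subjects without dementia by the end of the study, the time to conversion "will be censored at the date of last dementia diagnosis".

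Table 4 marks both the FAQ and disease staging at the regular 12- and 24-month visits (Visits 9 and 13). For subjects who stopped drug early, footnote b describes the return visits as "clinical assessments at 12 and 24 months as outlined above, at which efficacy (MMSE, CDR" and ADAS-cog14, then EQ-5D, QOL-AD, Zarit's Burden Interview, concomitant medications and adverse events. Nothing marks the list as examples. Neither the FAQ nor staging is in it.

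The body text is less specific. Section 9.3.3 describes the same visits as ones "at which efficacy and quality of life will be assessed along with concomitant medications and AEs", and the Synopsis and Section 9.5.5 say the same. The FAQ is described in Section 9.5.1.3, Efficacy Assessments: "FAQ: The study partner provides performance ratings (from 0 to 3) on 10 complex activities of daily living".

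**The concern.** The return visits keep outcome data after drug is stopped. Section 9.7.1.6.1 bases the primary analysis on intent to treat regardless of adherence, and the CDR is collected at these visits. The same holds for MMSE and ADAS-cog14. For the FAQ and for conversion to dementia, the footnote lets the subject come to the clinic and leave without the measurement.

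Two things are at stake. First, endpoints in one test sequence would treat discontinuation differently: three scales use observed off-drug 24-month values, while the FAQ rests mainly on model extrapolation from earlier visits. Second, conversion would be censored as a consequence of stopping drug. The listed reasons for stopping include inadequate therapeutic effect (Section 9.5.5), and some adverse events require stopping (Section 9.3.3). The censoring may therefore carry information about prognosis or treatment. A statistical analysis plan can model this gap but cannot recover data that were never collected.

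**Working it through.** **1. What is collected after early stopping (Table 4 and footnotes b and c).**

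| Visit | CDR, MMSE, ADAS-cog14 | FAQ | Disease staging |
|---|---|---|---|
| Early Discontinuation (ED), within 7 days of last dose | yes | yes | yes |
| Visit 14, 4 weeks after last dose | yes | yes | no |
| Visit 15, 12 weeks after last dose | yes | yes | yes |
| Off-drug 12 and 24 months | yes | not listed | not listed |

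The off-drug 12- or 24-month visit is waived if it falls within 8 days after ED or within 8 days either side of Visit 14 or 15.

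**2. The plan's own sample size, to fix what the 30% means.** Inputs from Section 9.7.2: difference 0.25 × 1.75 = 0.4375, SD 2.05, two-sided alpha 0.05, power 90%, dropout 30%.

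- Evaluable per arm: n = 2 × (1.960 + 1.282)² × 2.05² / 0.4375² ≈ 462 (463 with the exact t-test).
- Inflated: 462 / 0.70 = 660 per arm, 1320 in total (662 and 1324 with the exact t-test). The stated 1330 is reproduced to within 1%.
- Conversely, 665 × 0.70 = 465.5 evaluable per arm.

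The 30% is thus an allowance for a missing primary outcome. The protocol gives no rate of drug discontinuation, and no effect size, SD or event rate for the FAQ or for conversion. Power for those two endpoints cannot be computed.

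**3. How many subjects could be affected.** Assumption: the 30% is taken as drug discontinuation. Then 0.30 × 1330 = 399 subjects stop early.

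| Share returning at month 24 | Subjects at a 24-month visit without listed FAQ or staging |
|---|---|
| 25% | about 100 |
| 50% | about 200 |
| 75% | about 299 |
| 100% | 399 |

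These counts ignore the few visits waived under the 8-day rule.

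**4. Staging time lost.** The last planned staging is Visit 15, about 3 months after the last dose. For stopping at month d, the unstaged time to month 24 is max(0, 24 − (d + 3)).

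| Stops at month | Last staged about month | Unstaged to month 24 |
|---|---|---|
| 3 | 6 | 18 months |
| 6 | 9 | 15 months |
| 12 | 15 | 9 months |
| 18 | 21 | 3 months |

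With d uniform on 0 to 24 months (assumption), the mean loss is 21² / (2 × 24) = 9.2 months per discontinuer. As a share of planned time this is 0.30 × 9.2 / 24 = 11.5%. It is a ceiling: it counts every discontinuer as someone who would have returned, and none as having already converted.

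**The case against.** Several points on the other side stand.

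- A reader might infer that no early discontinuer has an FAQ at 24 months. Table 4 does not support that. The FAQ is done at ED and at Visits 14 and 15, so a subject who stops around month 21, around month 23 or just before month 24 has a value close to month 24.
- For the FAQ, the unqualified reference to efficacy in the Synopsis and Sections 9.3.3 and 9.5.5 can be read to include it. This is a conflict between text and footnote, not proof that the FAQ will be skipped. The argument does not help staging, which is not among the scales described in Section 9.5.1.3 and is not added to these visits elsewhere.
- It is tempting to set 465 per arm for the FAQ against 565 to 665 for CDR-SB. That turns the 30% allowance for a missing primary outcome into a drug-stopping rate. On the protocol's own use of the figure, CDR-SB also has about 465 per arm.
- A reader might also conclude that the hazard ratio for conversion is biased. That needs discontinuation to remain informative after covariate adjustment, and staging does continue for 12 weeks after the last dose. The documents fix neither direction nor size.
- The schedule shown belongs to Version 5.0 (Amendment 04). Part of the text, including the statistical sections, also appears with Amendment 05 marks and keeps both endpoints and the censoring rule. The schedule belonging to that version is not shown, so a later correction of the footnote cannot be excluded.

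**Conclusion.** The gap is real in the only schedule shown. Staging is not provided for at the off-drug 12- and 24-month visits. The FAQ is left out of the controlling footnote, in conflict with the body text. Followed as written, most early discontinuers have no 24-month FAQ, late stoppers excepted, and their time to dementia ends about 12 weeks after the last dose even if they attend at month 24. These two secondary endpoints therefore handle discontinuation differently from CDR-SB, ADAS-cog14 and MMSE, and conversion is exposed to possibly informative censoring of unknown direction and size.

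The harm is inconsistency and avoidable missing data. A shortfall against planned power has not been shown. The figures (up to 399 early stoppers, about 100 to 399 attending without these measurements, at most 11–12% of staging time) rest on reading the 30% dropout as drug discontinuation. The last figure also assumes uniform stopping.

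**What to change.** In Table 4 footnote b, add the FAQ and disease staging, with the existing central review, to the off-drug 12- and 24-month assessments. Footnote n already foresees remote input from the study partner: "At visits where the CDR or FAQ are conducted, the investigator will determine whether the study partner must attend in person" or can be reached by telephone. Name the same instruments in the Synopsis and Sections 9.3.3 and 9.5.5, so that text and footnote agree. Where Visit 14 replaces a 12- or 24-month visit under the 8-day rule, collect staging there as well, because Table 4 does not mark it at Visit 14. Check whether any later schedule carries the same text.

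The cost is a protocol amendment, slightly longer visits that already take place, and some additional central reviews and possible adjudications. One limit remains: a conversion first found at an off-drug visit is dated only to within up to about 12 months, against 3 months on the regular schedule. Such times are interval-censored and should be analysed with that in mind.

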9.5.1.6 Other Assessments

The NPI-10 item will be conducted at Visit 2 and then every 6 months. HRQoL will be measured using EQ-5D and QOL-AD at screening and every 6 months following randomization. In order to confirm the validity of the answers provided by the subject, the study partner will serve as subject’s proxy and complete the EQ-5D and QOL-AD to rate the subject’s HRQoL. In addition, the study partner will complete (self-report) their own EQ-5D. As a result, a set of 3 EQ-5Ds (1 from the subject; 2 from the study partner) and 2 QOL-ADs (1 from the subject; 1 from the study partner) will be provided at each visit. Additionally, the primary study partner burden will be measured using Zarit’s Burden Interview every 6 months to assess the stresses experienced by study partners.

At visits where the EQ-5D, QOL-AD, or Zarit’s Burden Interview are conducted, the investigator will determine whether the study partner must attend in person or whether telephone contact will be suitable, and will base this determination upon the functional ability of the subject amongst other factors.

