Urine pregnancy test (females of CBP only) ^k	X		X	X	X	X	X	X	X	X	X	X	X	X			X
Blood sample for viral characterization ^l	X																
Blood sample for storage for immune status ^m	X		X		X	X		X				X	X	X	X	X	X

Table 4 Schedule of Procedures/Assessments in Study E2609-G000-301

Phase	Randomization															UNS Visit ^d
	Treatment													Follow-Up		
Period	2	3	4	5	6	7	8	9	10	11	12	13	ED ^b	14 ^c	15 ^c	
Visit ^a																
Day	1	15	29	57	85	183	274	365	456	547	638	729		757	813	
Week	1	3	5	9	13	27	40	53	66	79	92	105		109	117	
Weeks elapsed since 1st dose	0	2	4	8	12	26	39	52	65	78	91	104		108	116	
Nominal months elapsed since 1st dose	0		1	2	3	6	9	12	15	18	21	24		25	27	
Procedures/ Assessments																
MMSE ⁿ	X					X		X		X		X	X	X	X	
CDR ⁿ	X				X	X	X	X	X	X	X	X	X	X	X	
ADAS-cog ₁₄ ⁿ	X					X		X		X		X	X	X	X	
FAQ ⁿ	X					X		X		X		X	X	X	X	
Disease Staging ^o					X	X	X	X	X	X	X	X	X		X	
NPI ₁₀	X					X		X		X		X	X		X	
C-SSRS	X											X	X			
Clinical assessment of suicidal thinking and behavior ^p		X	X	X	X	X	X	X	X	X	X			X	X	X
EQ-5D ^q						X		X		X		X	X			
QOL-AD ^r						X		X		X		X	X			
Zarit's Burden Interview of study partner						X		X		X		X	X			
MRI including vMRI and fMRI ^s								X				X	X			
Amyloid PET (optional substudy) ^t								X				X	X			
Telephone contact ^u		X	X		X	X		X		X		X	X			
Blood samples for PK ^v		X	X		X	X		X		X		X	X			
Blood samples for PD and exploratory biomarkers ^w	X	X	X		X	X		X		X		X	X	X	X	

Table 4 Schedule of Procedures/Assessments in Study E2609-G000-301

Phase	Randomization															ED ^b	Follow-Up		UNS Visit ^d
	Treatment																		
Period	2	3	4	5	6	7	8	9	10	11	12	13	14 ^c	15 ^c					
Visit ^a	1	15	29	57	85	183	274	365	456	547	638	729		757	813				
Day	1	3	5	9	13	27	40	53	66	79	92	105		109	117				
Week	0	2	4	8	12	26	39	52	65	78	91	104		108	116				
Weeks elapsed since 1st dose	0		1	2	3	6	9	12	15	18	21	24		25	27				
Nominal months elapsed since 1st dose	0		1	2	3	6	9	12	15	18	21	24		25	27				
Procedures/ Assessments																			
CSF sampling for PK and PD (optional substudy) ^x												X	X						
Adverse events	X	X	X	X	X	X	X	X	X	X	X	X	X	X	X	X			
Sleep/Dream Questionnaire ^y	X	X	X	X	X	X	X	X	X	X	X	X	X	X	X	X			
Possible Drug Abuse Potential Form/ Questionnaire ^z	X	X	X	X	X	X	X	X	X	X	X	X	X	X	X	X			
Randomization	X																		
Dispense study drug	X ^{aa}	X	X	X	X	X	X	X	X	X	X								

Notes:

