ADAS-cog₁₄ = Alzheimer’s Disease Assessment Scale - Cognitive subscale (14 items), CBP = child-bearing potential, CDR = Clinical Dementia Rating scale, CMV = cytomegalovirus, CNS = central nervous system, CSF = cerebrospinal fluid, C-SSRS = Columbia Suicide Severity Rating Scale, ECG = electrocardiogram, ED = Early Discontinuation, EQ-5D = EuroQol-5 Dimensions, FAQ = Functional Assessment Questionnaire (also known as the Functional Activities Questionnaire), fMRI = functional MRI (to be performed task free at resting state), HSV1 = herpes simplex virus 1 (orolabial herpes), HSV2 = herpes simplex virus 2 (genital herpes), INR = International Normalized Ratio, LP = lumbar puncture, MMSE = Mini Mental State Examination, MRI = magnetic resonance imaging, NPI = Neuropsychiatric Inventory, PBMC = peripheral blood mononuclear cell, PD = pharmacodynamics, PET = positron emission tomography, PK = pharmacokinetics, QOL-AD = Quality of Life in Alzheimer’s Disease, UNS = unscheduled, vMRI = volumetric MRI.

^a A window of ±3 days will be permitted for Visits 3 and 4. A window of ±7 days will be permitted for Visits 5 and 6. A window of ±10 days will be permitted for Visit 7 to 13 inclusive. A window of ±3 days will be permitted for the Follow-Up Visits. If use is made of the permitted visit windows, every effort should be made to bring the subject back in line with the “weeks elapsed since 1st dose” at subsequent visits.

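### The off-drug 24-month visit can be replaced by Visit 14 or 15, where EQ-5D, QOL-AD and Zarit are not scheduled, so a few exploratory 24-month values can be missed

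*Protocol*

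**What the plan says.** Section 9.5.1.6 sets the general rule for quality of life: "HRQoL will be measured using EQ-5D and QOL-AD at screening and every 6 months following randomization". Zarit's Burden Interview follows the same six-monthly rhythm.

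For subjects who stop study drug early, Table 4, footnote b (Section 9.5.2.1) adds return visits at 12 and 24 months, or at 24 months only if the drug was stopped after month 12. Besides MMSE, CDR and ADAS-cog14, it states that "quality of life (EQ-5D, QOL-AD and Zarit’s Burden Interview) will be assessed along with concomitant medications and AEs" at those visits.

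The same footnote then relaxes attendance. The 12- and 24-month visits "do not need to be attended if they fall within 8 days (visit window) after the ED Visit or within ±8 days". The second of these limits is measured from Visit 14 or Visit 15, whichever lies close enough.

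The timing of the possible replacement visits is also in footnote b. The subject "will undergo an ED Visit within 7 days of their last dose of study drug", and "Follow-Up Visits will be scheduled 4 and 12 weeks after the last dose of study drug".

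In the body of Table 4, the rows for EQ-5D, QOL-AD and "Zarit's Burden Interview of study partner" are marked at Visits 7, 9, 11, 13 and ED, and are blank at Visits 14 and 15. The CDR, MMSE and ADAS-cog14 rows are marked at ED, 14 and 15.

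Section 9.7.1.1.3 lists change from baseline at 24 months in EQ-5D, QOL-AD and Zarit as exploratory endpoints.

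**The concern.** The waiver makes sense only if the visit that replaces the 12- or 24-month assessment collects the same things. For the efficacy scales named in footnote b it does. For the three quality-of-life and burden instruments, the ED Visit is an adequate replacement, but Visits 14 and 15 are not. A site that follows the table as written would see the subject within 8 days of month 24, record the clinical scales, and skip questionnaires that the same footnote says are part of the assessment.

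At stake is avoidable missing data on named endpoints, confined to subjects who stopped study drug. Post-discontinuation visits exist to keep those subjects in an analysis made without regard to adherence. An SAP can define analysis windows, but it cannot recover a questionnaire that was never given, so this belongs in the protocol.

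**Working it through.** **Which version.** The protocol file contains text from more than one version. The schedule used here is Table 4 of Version 5.0 (Amendment 04). Text marked as revised under Amendment 05 is shown only from the end of Section 9.6 onward. It keeps the three endpoints (Section 9.7.1.1.3) but does not include its own Table 4.

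**Plan figures reproduced first.**
- Visit dates: 729 + 28 = 757 (Visit 14) and 729 + 84 = 813 (Visit 15), as in the Table 4 header.
- Sample size (used below only as a scale): with difference 0.25 × 1.75 = 0.4375, SD 2.05, two-sided 5% and 90% power, 462 per arm are needed; 462 / 0.70 = 660 per arm, total 1320. Section 9.7.2 states 1330, which is close enough.

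**Content of the visits, side by side.**

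| Visit | MMSE, CDR, ADAS-cog14 | EQ-5D, QOL-AD, Zarit |
|---|---|---|
| Off-drug 12/24-month (footnote b) | yes | yes |
| ED | yes | yes |
| Visit 14 | yes | no |
| Visit 15 | yes | no |

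**Which last-dose days trigger the gap at month 24.** Let L be the day of last dose. The visit is waived through Visit 14 if |L + 28 − 729| ≤ 8, and through Visit 15 if |L + 84 − 729| ≤ 8.
- Visit 14: L = 693 to 709, 17 days.
- Visit 15: L = 637 to 653, 17 days.
- Together 34 of 728 possible days; 34 / 728 = 4.7%.

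The same rule at month 12 (day 365) covers L = 329 to 345 and 273 to 289, again 34 days, but no listed endpoint is set at month 12.

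**How many subjects at month 24.** Assumptions, none of them in the protocol: last-dose days spread evenly over 24 months, nominal visit dates, and every discontinuer still on study at month 24. Section 9.7.2 gives 30% as a dropout rate for sample size. It is borrowed here as a rate of stopping study drug, with a range around it.
- 10%: 133 × 34 / 728 = 6.2
- 30%: 399 × 34 / 728 = 18.6
- 40%: 532 × 34 / 728 = 24.8

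**What earlier value remains.** The ED Visit takes place between L and L + 7.
- Replaced by Visit 14: from 729 − (709 + 7) = 13 to 729 − 693 = 36 days before month 24.
- Replaced by Visit 15: from 729 − (653 + 7) = 69 to 729 − 637 = 92 days before month 24.

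**The case against.** The case for leaving this alone has real weight. The endpoints are exploratory. The waiver permits non-attendance and does not require it, so some subjects will still come. An ED value should exist, and whether it may stand for month 24 is a question for the SAP, which is not shown. The trigger is where the last-dose date happens to fall, under one rule for both arms. All of this stands and keeps the point minor. It does not remove the mismatch between footnote b and its own table.

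It is also fair that the schedule comes from the Amendment 04 version. The gap may have been closed under Amendment 05. The documents cannot show this either way, so it is something to check.

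A reader might infer more than the documents support in four ways:
- **That about 19 subjects will be lost.** The 30% in Section 9.7.2 is dropout for sample size. Someone who leaves the study has no visit to waive. The protocol gives no rate for stopping drug while staying on study, so 19 is an upper bound at that rate.
- **That the loss doubles because month 12 is affected too.** The listed endpoints are at 24 months only, and a subject whose 12-month visit is waived is still asked back at month 24.
- **That the treatment comparison is biased, or that the primary result suffers.** Nothing in the documents shows bias between arms, and CDR is done at Visits 14 and 15.
- **That the 8 days in footnote b contradict footnote a**, which states "A window of ±10 days will be permitted for Visit 7 to 13 inclusive". Footnote a governs when scheduled visits may take place; footnote b governs when a separate off-drug assessment may be skipped. The two lengths need not agree. At most, the parenthetical label in footnote b is loosely worded.

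**Conclusion.** The point holds as a small inconsistency in data collection. In the latest schedule shown, footnote b allows Visit 14 or 15 to replace the off-drug 24-month assessment, although neither visit includes the EQ-5D, QOL-AD or Zarit that the assessment is meant to collect. The on-time value of three exploratory 24-month endpoints can then be missed in study-drug discontinuers who attend the clinic within 8 days of the due date.

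With evenly spread last doses, 4.7% of discontinuers who stay on study would be affected at month 24. That is at most about 19 of 1330 subjects at 30% discontinuation, with a range of 6 to 25 for 10% to 40%, and fewer to the extent that discontinuers leave the study or choose to attend anyway. The issue does not threaten the trial's conclusions. It is worth correcting because the remedy is so cheap.

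**What to change.** Add one sentence to Table 4, footnote b: when Visit 14 or 15 replaces the 12- or 24-month assessment, EQ-5D, QOL-AD and Zarit's Burden Interview are also administered at that visit. Alternatively, limit the waiver to the ED Visit, which already includes them. The first option is preferable because it adds no visit. Check that the Amendment 05 schedule carries the change. Footnote a can stay as it is.

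The cost is a footnote edit, a conditional eCRF form, and a few minutes of questionnaires at a visit that takes place anyway. Section 9.5.1.6 already lets the investigator decide whether the study partner contributes by telephone.
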